#### 2.6.1.3 Additional endpoints

FeNO is planned to be assessed at Visit 1 and 2 (screening), Week 6, Week 8, Week 10, Week 12/EOT, and for patients who do not enter the OLE, at EOS.

FeNO will be analyzed as raw data, absolute and percent change from baseline at each visit. Average FeNO from Week 6 to Week 12/EOT will also be computed for each patient; missing values will not be imputed and the average will be calculated whatever the number of missing data; the corresponding change from baseline will be derived.

If missing interim FeNO values (Week 6, Week 8, or Week 10), the graphical summaries of the missing patterns may be provided to examine if there is any different missing pattern between treatment groups.

The following endpoints will be considered as additional PD endpoints for the study:

- Absolute and percent change from baseline in FeNO at Week 12/EOT
- Absolute change from baseline in the averaged FeNO from Week 6 to Week 12/EOT

No imputation of missing data will be performed.

**Table 5 – Overview of the bronchoscopy and blood biomarkers assessed by matrix, technique and type of biomarkers**

	Bronchoscopy (baseline and Wk 12/EOT)			Blood (baseline, Wk 6, Wk12/EOT)
	Biopsy (6-8 fragments/visit)	Brushing (4-6 samples/visit)	BALF (4 x 50 mL/visit)	
Immuno-histochemistry / Immuno-cytochemistry	Eosinophils (MBP) a Mast cells a (Tryptase, Chymase) T lymphocytes (CD3) a T helper cells (CD4) a Goblet cells (MUC5) a B cells (CD23) a	Eosinophils (MBP) e Mast cells e (Tryptase) Macrophages e (CD206, CD68) B cells (CD23) e	Eosinophils (MBP) e Mast cells e (Tryptase) Macrophages e (CD206, CD68) B cells (CD23) e	-
Histology/cytology	Subepithelial thickness b	-	Differential cell count c	Differential cell count f (baseline, Wk 12/EOT)
RNA	RT-qPCR panel g Microarray i	RT-qPCR panel g Microarray i	RT-qPCR panel g Microarray i	RT-qPCR panel g (baseline only) Microarray (baseline only) i
Proteins	-	Th2 panel: 15-LO1, GPX4, LC3, iNOS, DUOX2, FOXA3 h	Periostin Eotaxin-3 MCP-4 TARC Cytokines : IL-6, IFN- $\gamma$ , TNF- $\alpha$	Periostin Eotaxin-3 MCP-4 TARC PARC ECP Total IgE and regional specific IgE panels d Cytokines : IL-4, IL-5, IL-6, IL-13, IFN- $\gamma$ , TNF- $\alpha$

- a* Following parameters are provided by the lab : total area of tissue assessed, total positive area, number of positive cells; all assessments made in triplicate
- b* Following parameters are provided by the lab: Number of tissue fragments in paraffin-embedded block, total area of tissue measured, total length of epithelium assessed, area of smooth muscle, thickness of basement membrane in 3 locations; all assessments made in triplicate
- c* Following parameters are provided by the lab: Total cell counts as well as neutrophil, eosinophil, lymphocyte, macrophage, epithelial, mast cell counts
- d* See [Appendix C](#) for the list of regional specific IgE panels; assessed at Visit 2 and Week 12/EOT only
- e* Following parameters are provided by the lab: absolute cell number, absolute number of stained cells, total number of inflammatory cells
- f* Part of the standard White Blood Cell differential cell count: total white blood cell count, neutrophils, eosinophils, basophils, monocytes and lymphocytes
- g* See [Appendix D](#) for the panel of Th2-related genes tested
- h* The value of protein expression will be standardized and background-subtracted
- i* Details about  $\mu$ array data as well as their statistical analyses will be provided in a separate statistical analysis plan

## **2.6.2 Description of the analyses**

Bronchoscopy biomarkers will be analyzed on the bronchoscopy PD population and blood biomarkers and FeNO on the secondary PD population.

### **2.6.2.1 Bronchoscopy procedure**

The following numbers and % of patients from the bronchoscopy PD population will be provided by treatment group and by visit:

- Patients with a bronchoscopy performed.
- Patients with a biopsy collected.
- Patients with a biopsy evaluable.
- Patients with a BALF sample collected.
- Patients with a BALF sample evaluable.
- Patients with a brushing sample collected.
- Patients with a brushing sample evaluable.

The location of the biopsy, the BALF sample and the brushing sample (right upper lobe, right middle lobe, right lower lobe, left lower lobe, lingula, left upper lobe) will be also summarized by treatment group and visit.

For the biopsy samples, descriptive statistics (mean, SD, standard error of the mean [SEM], median, Q1, Q3, and range) of the total area of tissue assessed (averaged across the triplicate measurement) will be provided by treatment group and by visit.

### **2.6.2.2 Descriptive statistics**

The descriptive statistics (mean, SD, SEM, median, Q1, Q3, and range) for all biomarkers collected, as well as for the main, exploratory and additional PD endpoints, will be provided by treatment and time point on raw data, absolute changes and percent changes from baseline. The number of imputed values will also be presented when applicable. The descriptive statistics may also be further sub-grouped by region or ICS if need be.

Boxplots will also be provided by treatment and time point. Time profile plots of raw data, absolute and percent change from baseline and ratio from baseline (mean  $\pm$  SEM and/or median with interquartile range) will also be produced by treatment group when applicable.

For each type of inflammatory cell in the biopsy, BALF (measured by ICC or cytology) and brushing samples, the number and % of patients with no positive cell and those with positive cells will be also provided by treatment group and visit. The number and % of patients with no positive cell and those with positive cells at Week 12/EOT will be also provided according to the baseline status (with or without positive cell), by treatment group.

### **Note about allergen-specific IgE measures**

The descriptive statistics for regional specific IgEs at each visits and corresponding plots will be performed only on patients who are sensitized to the specific allergen at baseline using two thresholds:

- Positive baseline result, ie,  $\geq 0.35$  IU/mL.
- Baseline result above the LLOQ, ie,  $\geq 0.1$  IU/mL.

### **2.6.2.3 Main analysis: pharmacodynamic analyses**

The objective of the PD analyses is to compare the post-baseline levels of biomarkers between dupilumab and placebo.

#### **Analysis of the main PD endpoints**

For each inflammatory cell measured in biopsy samples by IHC, a formal statistical modeling will be performed on both absolute change from baseline and ratio from baseline for the number of positive cells/mm^2 as well as for the two other ratios defined on goblet cells:

- The absolute change from baseline will be compared at Week 12/EOT between dupilumab and placebo using a linear fixed-effect model using SAS© Mixed procedure, with treatment, region and ICS dose level as fixed effects, and the baseline value as continuous covariate. The difference between dupilumab and placebo in least square (LS) mean change from baseline, the corresponding two-sided 90% confidence interval (CI), and p-values will be reported.
- The ratio from baseline will be first log-transformed; the log of the ratio will be compared at Week 12/EOT between both treatment groups using a linear fixed effect model using SAS© Mixed procedure, with treatment, region and ICS dose level as fixed effects, and the log of the baseline value as continuous covariate. Estimates and 90% CIs for the geometric mean of the ratio between treatments and p-values will be obtained by computing estimates and 90% CIs for the differences between LS-means within the linear fixed-effect model framework, and then converting to ratios by the antilog transformation.

The analysis of the residuals will be primarily based on plots of studentized residuals. In case of major deviation to the statistical assumptions (normality of the distribution for instance), a rank-based analysis of covariance (rank ANCOVA) model adjusted for baseline, region and ICS dose will be used instead to compare the main PD endpoints between dupilumab and placebo. P-values comparing the treatment groups will be provided. In case of convergence issues and given the low sample size, some fixed effects (e.g., region, ICS dose) might be removed from the model.

No imputation will be performed for missing values.

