### 2.6.1.1 Main endpoints

The following inflammatory cells measured in biopsy samples by IHC will be considered as the main markers:

- Eosinophils, based on major basic protein (MBP) positive cells; the hypothesis is that dupilumab will decrease tissue eosinophils in patients with persistent asthma compared to placebo, as it was demonstrated in the R668-PH-17214 study that dupilumab potently blocked house dust mite-induced eosinophil infiltration into the lungs of *Il4rahu/hu Il4hu/hu* mice.
- Mast cells: tryptase positive, chymase positive.
- T lymphocytes: CD3 positive.

- T helper cells: CD4 positive.
- Goblet cells: MUC5 positive.
- B cells: CD23 positive.

The main endpoints will be the absolute change from baseline, the percent change from baseline as well as the ratio from baseline at Week 12/EOT for:

- The number of positive inflammatory cells per mm^2, derived by the biostatistics department, for each marker described above as:

$$\frac{\text{Number of positive inflammatory cells}}{\text{Total area of tissue assessed in mm}^2}$$

- For goblet cells (MUC5 positive) only, the following ratios will be also calculated by the biostatistics department:

- $\frac{\text{Total positive area assessed in mm}^2}{\text{Total area of tissue assessed in mm}^2}$
- $\frac{\text{Number of positive inflammatory cells}}{\text{Total positive area assessed in mm}^2}$

All IHC measurements will be assessed in triplicate; the mean of the 3 values will be used for all statistical analyses. Of note, the previous ratios will be calculated for each replicate first and then the 3 replicates will be averaged (the missing values will not be imputed and the average of the replicates will be calculated whatever the number of non missing values)

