### 2.11.2 Data handling conventions for PD biomarkers

For biomarkers with nonnumeric values, the imputed values used for the descriptive statistics will be determined by considering the following rules:

- If database value is < LLOQ, the value used will be LLOQ/2
- If database value is > ULOQ, the value used will be the ULOQ

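### The log-ratio model for the main biopsy endpoints has no value for a patient with no positive cell, so such patients drop out and the reported fold change can be too small

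*SAP*

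**What the plan says.** Section 2.6.2.3 of the SAP (Analysis of the main PD endpoints) states that for each biopsy cell type "a formal statistical modeling will be performed on both absolute change from baseline and ratio from baseline". For the second model, "The ratio from baseline will be first log-transformed; the log of the ratio will be compared at Week 12/EOT between both treatment groups", with treatment, region and ICS dose as fixed effects "and the log of the baseline value as continuous covariate". The result is converted back to a ratio of geometric means with a 90% CI and a p-value. If residual plots show a major departure from assumptions, "a rank-based analysis of covariance (rank ANCOVA) model adjusted for baseline, region and ICS dose will be used instead", and for that fallback only p-values are promised. Missing values are not imputed.

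Section 2.6.1.1 defines the endpoint as positive cells divided by tissue area, computed per replicate; "the mean of the 3 values will be used for all statistical analyses". For eosinophils alone it states a direction: "the hypothesis is that dupilumab will decrease tissue eosinophils in patients with persistent asthma compared to placebo".

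Section 2.6.2.2 announces, for biopsy, BALF and brushing, that "the number and % of patients with no positive cell and those with positive cells will be also provided by treatment group and visit", and cross-tabulates Week 12 status by baseline status.

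The only substitution rule is in section 2.11.2, which begins "For biomarkers with nonnumeric values, the imputed values used for the descriptive statistics will be determined by considering the following rules". It sets results below the LLOQ to half the LLOQ and results above the ULOQ to the ULOQ.

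**The concern.** A patient with no positive cell has a density of 0. At Week 12 this makes the response log(0). At baseline the ratio is a division by zero and the covariate is log(0). The SAP plans to count these patients but never says how they enter the log-ratio model. A counted 0 is numeric, the SAP gives no LLOQ for IHC counts, and section 2.11.2 is worded for descriptive statistics, so that rule does not reach them.

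Run as written, the software treats the undefined logarithm as missing and leaves the patient out. If dupilumab lowers tissue eosinophils as hypothesised, Week 12 zeros occur more often on dupilumab and belong to strong responders. Dropping them pulls the estimated fold towards 1. No direction can be claimed for the other markers.

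At stake is the fold change in tissue eosinophils, the scale on which section 1.3 judges 21 patients per group sufficient for the biopsy endpoints. The log-ratio p-values also enter the false discovery rate adjustment for biopsy IHC. The exploratory analyses in section 2.6.2.3 carry the same model to the BALF and brushing ICC ratios and the BALF cell counts. Two endpoints have a further problem: goblet cells per positive area and CD206/CD68 are undefined, before any logarithm, when their own denominator is zero.

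**Working it through.** **The plan's own figure.** Section 1.3 gives an SD of the log ratio of 1.7, a 3.8-fold decrease, 21 per group, a one-sided 5% test and 80% power. The effect size is ln(3.8)/1.7 = 1.335/1.7 = 0.785. The noncentrality is 0.785 × √(21×21/42) = 2.54 on 40 degrees of freedom, and the noncentral t distribution gives 80.4%. The stated 80% is reproduced.

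**Loss of numbers alone.** Suppose 28% of dupilumab and 15% of placebo patients are lost (first row of the table below). That leaves 21 × 0.72 ≈ 15 and 21 × 0.85 ≈ 18. With the effect unchanged, the noncentrality is 0.785 × √(15×18/33) = 2.25 on 31 degrees of freedom, and power is 71.0%. Selection of responders comes on top.

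**Zeros dropped against a constant added.** The SAP gives no cell counts, so count levels are assumed. The simulation used:
- 21 per arm and a true 3.8-fold fall;
- Poisson counts on lognormal densities, with tissue area varying by visit (log SD 0.3);
- covariance analysis of the log ratio on treatment and log baseline, one-sided 5%.

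Two settings keep the log-ratio SD at 1.7: log SD 1.7 at each visit (correlation between visits 0.50) and log SD 1.5 (correlation 0.36). The constant is half the smallest non-zero value, added to every value.

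| Median baseline count, all replicates together | Dropped on dupilumab | Fold, zeros dropped | Power, zeros dropped | Power, constant added |
|---|---|---|---|---|
| 10 | 26-28% | 2.7 | 67-71% | 83-86% |
| 30 (10 in each of 3 independent replicates) | 9-12% | 3.2-3.3 | 80-85% | 87-89% |
| 50 | 6-7% | 3.3-3.5 | 83-87% | 87-90% |

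The first two rows differ because a patient's mean is zero only if every available replicate is zero. On placebo, 12-15% are dropped in the first row.

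The correlation between visits matters. At 0.62 (baseline log SD 1.2, log-ratio SD 1.5), power at a count of 10 is 64% with zeros dropped against 80% with the constant. At 50 it is 80% against 85%, with a fold of 3.30, which is the lower end in the last row. With no correlation, power at 10 is 85% against 93%.

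**Type I error.** Under no effect the rejection rate was 4.8-5.6% with zeros dropped and 4.7-5.7% with constants, so it is not inflated.

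**Dependence on the constant.** At a count of 10 the true 3.8-fold fall is estimated at about 3.4 to 3.5-fold when half the smallest value is added, and about 3.0 to 3.1-fold when the smallest value is added. In a separate run (median 10 cells/mm² over 1 mm²), replacing only the zeros by 0.01 gave 6.3-fold.

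**Reach in the multiplicity family.** There are seven stains (MBP, tryptase, chymase, CD3, CD4, MUC5, CD23) plus two further goblet ratios. Nine endpoints in two models each give 9 × 2 = 18 p-values in the biopsy IHC group, of which 9 come from the log-ratio model.

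**The case against.** The strongest reply is that zeros may be rare in biopsy. The table in section 2.6.2.2 covers biopsy, BALF and brushing together and gives no rate, triplicates make a zero mean less likely, and section 1.1 allows no more than 8 patients with blood eosinophils below 150 cells/µL. This stands as a limit on size, and the second and third rows of the table show it. It does not give the undefined logarithm a value.

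Second, the rank fallback could be applied to the ratio. A Week 12 zero then takes the lowest rank and only baseline zeros are lost; power at a count of 10 is about 75-80%. This partly protects the p-value. But the trigger is the residual plots, and patients already dropped leave no residuals. The fallback also gives no fold change.

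Third, with no imputation of missing values, the plan can be read as a complete-case analysis, so nothing is left to the analyst. That may be how it would run. But a counted zero is an observed value, and complete-case handling is what produces the attenuation.

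Fourth, section 2.6.1 refers to the LLOQ rules for PD variables without limiting them to descriptive statistics. That would help only if the laboratory reported an empty biopsy as below the LLOQ, which the SAP does not say.

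Fifth, the formal sample size rests on FeNO, and the 3.8-fold calculation is supporting evidence. This is correct and limits the weight of the point.

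**Conclusion.** The defect holds: one of the two planned models for the main biopsy endpoints is undefined for patients whom the SAP itself expects to count. That conclusion needs no assumed rate. Its size does. With zeros dropped, a true 3.8-fold fall is reported as about 2.7-fold, with a loss of about 15 to 16 points of power, if the summed median baseline count is 10. At 10 per replicate it is about 3.2 to 3.3-fold with 4 to 7 points lost, and at a summed 50 about 3.3 to 3.5-fold with 3 to 4 points lost. These figures rest on Poisson counts, lognormal densities and the visit correlations shown.

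A reader might infer that the main analysis as a whole fails, that false positives increase, or that power will in fact fall to about two thirds. The document supports none of these. The absolute-change model for cells/mm² keeps every zero, type I error is preserved, the study is exploratory, and no count level is given. The point should be fixed before unblinding, as a gap in one model.

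**What to change.** Amend the SAP before unblinding:

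1. For any marker with a zero, add one pre-specified constant to the patient-visit value, after averaging replicates, for all patients at both visits. Use it in both the log ratio and the log-baseline covariate. Half the smallest non-zero value in the pooled blinded data is a workable choice. Apply the same rule, in each endpoint's own units, to the goblet area fraction, the BALF and brushing ICC ratios and the BALF count ratios.
2. As sensitivity analyses outside the Benjamini-Hochberg family, repeat with one smaller and one larger constant, so that the dependence of the fold is seen in both directions.
3. Print the number of zeros by arm and visit beside each fold estimate.
4. For goblet cells per positive area and CD206/CD68, analyse only patients with a non-zero denominator at both visits, label the result conditional, and give the exclusions by arm.

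The cost is a few sentences and minor programming. The drawback is that the fold depends on the constant and stays somewhat attenuated when counts are low. At a median of 3 cells, half the smallest value still gives only 2.7 to 3.0-fold for a true 3.8, against 2.1 to 2.2-fold with zeros dropped.

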#### **Analysis of the additional PD endpoints**

The absolute change from baseline in FeNO will be analyzed using a mixed-effect model with repeated measures (MMRM) approach on the secondary PD population. All post-baseline data

until Week 12/EOT will be taken into account. The model will include the fixed categorical effects of treatment group (dupilumab vs placebo), visit and treatment-by-visit interaction, the ICS dose and the region, as well as the continuous fixed covariate of baseline FeNO value and the baseline FeNO-by-visit interaction. This model will be run using SAS® Mixed procedure with an unstructured correlation matrix to model the within-patient errors. Parameters will be estimated using restricted maximum likelihood method with the Newton-Raphson algorithm. Denominator degrees of freedom will be estimated using Kenward-Roger adjustment. The difference between dupilumab and placebo in LS-mean change from baseline at Week 12/EOT, the corresponding two-sided 90% CI, and p-values will be reported from this model.

This model will also provide the difference between dupilumab and placebo in LS-mean change from baseline in average FeNO from 6-12 weeks, using appropriate contrast. The difference in LS mean change from baseline, the corresponding 90% CI and p-values will be reported.

A similar model will be applied to the percent change from baseline in FeNo, and the difference between dupilumab and placebo in LS-mean percent change from baseline at Week 12/EOT, the corresponding two-sided 90% CI, and p-values will be reported from this model.

The analysis of the residuals will be primarily based on plots of studentized residuals. In case of major deviation to the statistical assumptions (normality of the distribution for instance), other approaches might be considered, such as the ANOVA-type or MMRM on transformed data.

If MMRM model fails to achieve convergence due to complexity of model specification, and given the low sample size, some fixed effects (e.g., region, ICS dose level) or interactions might be removed from the model; other covariance structures may be also tested.

No imputation will be performed for missing values.

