### **2.2.1 Pharmacodynamic populations**

Two PD populations will be defined:

- The bronchoscopy PD population will encompass all randomized and treated patients with an evaluable bronchoscopy performed at baseline and at Week 12/EOT; this population will be used for the analyses of the bronchoscopy PD endpoints;
- The secondary PD population will encompass all randomized and treated patients; this population will be used for the analyses of other PD endpoints.

Patients treated without being randomized will not be included in any PD populations.

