## **2.6 ANALYSIS OF PHARMACODYNAMIC VARIABLES**

Pharmacodynamic analyses will be performed on the bronchoscopy or on the secondary PD population, depending on the biomarkers.

All values will be assigned to the theoretical visit; unscheduled visit measurements will be included in the computation of baseline if occurred before the 1st IMP, but will not be included in any by-visit summaries or statistical models (only scheduled values will be taken into account).

Only data measured before or on the last IMP date + 14 days (on-treatment period) will be taken into account in all analyses.

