### **Analysis of the exploratory PD endpoints**

For biomarkers measured only once post-baseline, a linear fixed-effect model or a rank ANCOVA will be performed similarly to the analyses of the main PD endpoints, on the exploratory PD endpoints (absolute change from baseline and ratio from baseline for markers measured by ICC in BALF and brushing samples, and for different cell counts in BALF; absolute and percent change from baseline for the subepithelial thickness and protein levels; change in gene expression).

For biomarkers measured only twice post-baseline (proteins in blood), a MMRM (or other statistical approaches in case of deviations to the model assumptions) will be performed similarly to the analyses of the additional PD endpoints.

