## 2.7.2 Analyses

The change from baseline in efficacy parameters will be analyzed using a MMRM approach based on the secondary PD population. All on-treatment data until Week 12/EOT will be taken into account, i.e., data measured before or on the last IMP date + 14 days. The model will include the fixed categorical effects of treatment group (dupilumab vs placebo), visit and treatment-by-visit interaction, the ICS dose level and the region, as well as the continuous fixed covariate of baseline efficacy endpoint and the baseline-by-visit interaction. This model will be run using SAS© Mixed procedure with an unstructured correlation matrix to model the within-patient errors. Parameters will be estimated using restricted maximum likelihood method with the Newton-Raphson algorithm. Denominator degrees of freedom will be estimated using Kenward-Roger adjustment. The between-group difference (dupilumab vs placebo) in LS-mean change from baseline at each visit the corresponding two-sided 90% CI, and p-values will be reported from this model.

If MMRM model fails to achieve convergence due to complexity of model specification, and given the low sample size, some fixed effects or interactions might be removed from the model; other covariance structures may be also tested.

No imputation will be performed for the MMRM model.

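### The SAP states two data cut-offs for the FeNO and blood-protein repeated-measures models without saying which prevails, and the stricter one, read literally, can drop completers seen late in the Week 12 window (minor).

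*SAP*

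**What the plan says.** The opening of SAP 2.6, which covers all pharmacodynamic variables, sets a limit tied to the last dose: "Only data measured before or on the last IMP date + 14 days (on-treatment period) will be taken into account in all analyses".

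Within the same section, 2.6.2.3 (additional PD endpoints) describes the FeNO MMRM. Its data scope is "All post-baseline data", bounded by a visit and not by a dose: "until Week 12/EOT will be taken into account. The model will include the fixed categorical effects of treatment group (dupilumab vs placebo), visit". The paragraph neither restates nor cites the on-treatment limit.

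The blood-protein MMRMs take their specification from the FeNO model; they "will be performed similarly to the analyses of the additional PD endpoints".

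The analysis set does not remove early stoppers: "The secondary PD population will encompass all randomized and treated patients; this population will be used for the analyses of other PD endpoints". Missing FeNO values are left missing: "No imputation will be performed for missing values".

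The efficacy MMRM in 2.7.2 has almost the same structure and carries the limit in its own text: "All on-treatment data until Week 12/EOT will be taken into account, i.e., data measured before or on the last IMP date + 14 days".

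**The concern.** One rule is anchored to the last dose and the other to a visit. Where a value lies more than 14 days after the last dose but no later than Week 12/EOT, 2.6 excludes it and the FeNO paragraph, read alone, includes it. One programmer working from the model paragraph and another working from the section opening could build different data sets, and both could point to the text.

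The choice also changes what is estimated. On-treatment data describe the effect while on drug, and all post-baseline data describe the effect whether or not drug was stopped. The FeNO descriptive tables (2.6.2.2) and the eosinophil–FeNO correlations (2.6.2.7) follow 2.6, so they could rest on different records from the modelled FeNO difference. FeNO is also the endpoint on which the sample size in 1.3 was calculated.

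**Working it through.** **1. Which records the rules treat differently**

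*Patients who stop IMP early and are still measured.* FeNO is scheduled at Weeks 6, 8, 10 and 12/EOT (2.6.1). For example, take a last dose at Week 4 with all later visits attended. Week 6 is at +14 days and is kept by both rules. Weeks 8, 10 and 12 are at +28, +42 and +56 days, so 2.6 drops them and the FeNO paragraph keeps them. The disposition list in 2.1.1 counts stopping treatment separately from leaving the study, so such patients are conceivable. The SAP does not say how many to expect, or what visits they would attend.

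*Completers seen late in the window.* Dosing is every 2 weeks for 12 weeks (1.1), and a postponed EOT visit at Week 14 or 16 may bring up to two further doses (1.4). From this I infer a last regular dose at Week 10. The exposure formula in 2.4.1 agrees: 70 days from first to last dose + 14 = 84 days = 12 weeks. Nominal Week 12 is therefore exactly last dose + 14 days. Figure 1 allows ±3 days. With the last dose on its nominal day, a visit 1, 2 or 3 days late falls at +15, +16 or +17 days. These values are excluded under 2.6 read literally and included under the FeNO paragraph.

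**2. The plan's own power figure**

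Inputs from 1.3: difference 25 ppb, SD 32 ppb, one-sided 5% t-test, 21 completers per group.

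Noncentrality = 25 / (32 × √(2/21)) = 2.53. With 40 degrees of freedom the critical value is 1.684, and power is 80.1%. The stated 80% is reproduced.

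**3. Worst-case illustration of the early-stopper difference**

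Assumptions not in the SAP: k of the 21 dupilumab patients have their Week 12 FeNO off drug and keep none of the effect, no placebo patient is affected, and Week 12 is analysed alone.

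- All-data rule, with p = k/21: difference = 25 × (1 − p); dupilumab variance = 32² + p(1 − p) × 25².
- On-treatment rule: difference stays at 25 ppb, with 21 − k against 21 patients.

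For k = 2:

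- All data: 25 × 19/21 = 22.6 ppb; dupilumab SD = √(1024 + 0.0862 × 625) = 32.8; standard error = √(32.8²/21 + 32²/21) = 10.0; noncentrality 2.26; power 71.8%.
- On-treatment: standard error = 32 × √(1/19 + 1/21) = 10.1; noncentrality 2.47; power 78.2%.

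| k of 21 | All data: difference | All data: power | On-treatment: difference | On-treatment: power |
|---|---|---|---|---|
| 0 | 25 ppb | 80.1% | 25 ppb | 80.1% |
| 1 (5%) | 23.8 ppb | 76.1% | 25 ppb | 79.2% |
| 2 (10%) | 22.6 ppb | 71.8% | 25 ppb | 78.2% |
| 4 (19%) | 20.2 ppb | 62.7% | 25 ppb | 75.9% |

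The gap narrows if stoppers keep part of the effect. If the same share of patients is affected in both arms and dupilumab stoppers keep half the effect, a 10% share gives an expected all-data difference of 25 × (1 − 0.10 × 0.5) = 23.75 ppb. The MMRM also borrows from Weeks 6 to 10, so the on-treatment power loss shown is an upper bound.

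**The case against.** The strongest reply is that there is no real conflict. The FeNO paragraph is a subsection of 2.6, whose opening rule covers all analyses. On that view 2.6 sets the filter, and the FeNO sentence only says which visits enter the repeated-measures model. Its visit bound has a purpose of its own, because FeNO is also measured at EOS (2.6.1.3). In addition, the opening of 2.6 keeps unscheduled values out of the models. If the FeNO sentence overrode that opening, unscheduled FeNO values would enter too, which nobody would suppose was meant. This largely stands: the opening rule is the more natural governing text. What remains is that one sentence says only, the other says all, and neither gives way to the other.

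A reader might infer from the explicit on-treatment wording in 2.7.2 that the SAP deliberately chose a different rule for FeNO. The documents do not support that. Section 2.7 has no opening data rule of its own, so 2.7.2 has to state the limit itself, whereas 2.6.2.3 sits under one.

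A reader might also infer that the 80% power is wrong. It is not. Section 1.3 defines the 21 per group as completers and sets early dropout aside, so placing stoppers among those 21 illustrates sensitivity and does not test the stated figure.

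Finally, it is fair that the SAP does not show that off-drug FeNO visits will occur; the schedule after early stopping is normally a protocol matter. But the two rules need not agree even if nobody stops early, because the late-in-window completers remain.

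**Conclusion.** The point holds as a minor clarification. Read literally, the SAP gives two data rules for the FeNO MMRM and, by reference, for the blood-protein MMRMs, and it states no precedence. The 2.6 rule probably governs. That rule in turn has an edge problem: with an inferred Week 10 last dose it can exclude Week 12/EOT values from completers seen 1 to 3 days late but within the window.

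The size cannot be fixed from the document, because no discontinuation rate and no distribution of visit timing are given. In the assumed worst case, 1 to 4 affected dupilumab patients would lower the expected FeNO difference by 1.2 to 4.8 ppb under the all-data rule. With no affected record of either kind, the rules give the same result. The consequence is limited further because FeNO is classed as an additional endpoint, the main endpoints are biopsy cell counts, and the trial is exploratory.

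**What to change.** Three wording changes, made before database lock:

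1. In 2.6.2.3 (additional PD endpoints), describe the FeNO model's data as all on-treatment data until Week 12/EOT, and cross-refer to 2.6 for the definition.
2. State that the same scope governs the blood-protein MMRMs.
3. In 2.6, state that, for analysis, a Week 12/EOT value taken within the protocol visit window after the last planned dose counts as on-treatment even if it falls more than 14 days after that dose. Without this, the first change would write the loss of valid Week 12 values from completers into the FeNO model.

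A supportive FeNO run on all post-baseline values, on or off IMP, is optional; it would show the other effect, labelled as such.

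The cost is a few sentences and, if chosen, one extra model run. No new data or patients are needed. Values from early stoppers taken more than 14 days after their last dose would appear only in the supportive run, if it is done.
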